#### **Creatinine method evaluation**

Precision: The following statistics will be calculated for within and between batch precision: mean, SD and %CV. A CV less than 20% will be deemed acceptable.

Accuracy: All samples will be analysed in duplicate and the results averaged. Passing-Bablok regression and Pearson correlation coefficient will be used to compare and assess correlation of the results obtained from each method. Bland-Altman analysis will assess agreement and determine presence of any bias between the results obtained from the different methods. 95% confidence intervals will be calculated. Statistical analysis will be performed using the Analyse-It add-in for Microsoft Excel.

Linearity: The diluted creatinine standards will be analysed in duplicate and plotted against the concentration to give the  $r^2$  value. Means should be within 15% of each other to confirm linearity.

LLOQ: Mean, SD and %CV will be calculated. LLOQ will be defined as the level with a between batch precision of <15%.

Recovery: Each level of QC will be run in triplicate and the average calculated, with the recovery being expressed as a percentage with an acceptability of 100±20%.

Carryover: The % carryover from high to low concentrations will be determined. Differences of ±15% will be deemed acceptable.

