### **Creatinine method evaluation**

Method comparison will be performed by comparing creatinine results obtained by enzymatic assay on the Roche platform with results obtained by LC-MS/MS. A minimum of 50 patient samples will be analysed, as well as EQA samples. Within and between batch precision will be performed by loading Mitra® devices with IQC sample. 3 levels of IQC will be run a minimum of 5 times within the same analytical run and between analytical runs, on different days. Precision studies will be used to determine the LLOQ. Low patient pools will be prepared to give appropriate concentrations. Samples will be analysed 10 times within the same analytical run and 10 times between runs.

Linearity will be determined by performing dilutions of the creatinine standard material to prepare an extended standard curve. To assess recovery, blank samples will undergo sample preparation steps and will be spiked with the 3 different levels of creatinine QC. Carryover will be assessed by analysing an alternating high creatinine concentration sample with repeated analysis of a low creatinine or blank sample.

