#### **Data Analysis**

Statistical analysis will be performed based on CSLI recommendations and departmental protocols.

Study population characteristics (including patient age, tacrolimus dose, time since transplantation, haematocrit) will be expressed as median (range).

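### The creatinine between-batch precision limit is looser at the IQC levels (CV below 20%) than the limit that defines the LLOQ (below 15%), and the protocol gives no reason

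*Protocol*

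**What the plan says.** The acceptance limits are in the Protocol, Data Analysis, Creatinine method evaluation. For precision, the mean, SD and %CV are calculated both within and between batches, and then "A CV less than 20% will be deemed acceptable". For the LLOQ, "LLOQ will be defined as the level with a between batch precision of <15" per cent. For recovery on QC material the plan reads "with the recovery being expressed as a percentage with an acceptability of 100±20" per cent. Linearity and carryover in that section use 15%, as do stability and haematocrit under Sample collection comparison.

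The experiments are described in the Methodology section under the same heading. For the IQC, "Within and between batch precision will be performed by loading Mitra® devices with IQC sample", and "3 levels of IQC will be run a minimum of 5 times within the same analytical run and between analytical runs, on different days". The LLOQ is to come from precision studies on other material: "Low patient pools will be prepared to give appropriate concentrations", and "Samples will be analysed 10 times within the same analytical run and 10 times between runs".

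The only stated basis for the criteria is general: "Statistical analysis will be performed based on CSLI recommendations and departmental protocols".

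**The concern.** The LLOQ is the lowest concentration at which the assay is still precise enough to report a number. Relative imprecision usually grows as concentration falls towards that point, so the CV tolerated at the IQC levels would normally be no larger than the CV that marks the LLOQ. Here it is larger.

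At stake is the meaning of a pass. Developing and validating the LC-MS/MS method is the first item under Objectives and Specific Aims, and these are stated pass/fail limits for it. As written, the creatinine assay can be declared acceptably precise at a CV that the LLOQ rule rejects.

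**Working it through.** **Step 1: the two limits side by side**

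| | IQC precision | LLOQ |
|---|---|---|
| Statistic | between-batch %CV (within-batch also) | between-batch %CV |
| Limit | below 20% | below 15% |
| Material | IQC loaded on Mitra devices, 3 levels | low patient pools; device loading not stated |
| Between-run replicates | at least 5 per level | 10 |

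No figure in the plan is derived from these limits, so there is nothing to reproduce. The comparison is direct: 20% exceeds 15% by 5 percentage points, a ratio of 20/15 = 1.33 in CV and 1.33² = 1.78 in variance. The affected band is a between-batch CV from 15% to just under 20%.

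**Step 2: how often each rule would pass the same imprecision**

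The protocol gives no expected CV, so the true CVs below are assumptions. With normal data and the mean treated as fixed, the probability that an observed CV from n replicates falls below limit L when the true CV is t is

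P = Pr{χ² with n−1 df < (n−1)(L/t)²}.

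The replicate counts are read as 5 between-run results per IQC level and 10 per pool. One IQC level is compared with one pool.

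| Assumed true CV | IQC level, L = 20%, n = 5 | Pool, L = 15%, n = 10 |
|---|---|---|
| 16% | 4(20/16)² = 6.25, P = 0.82 | 9(15/16)² = 7.91, P = 0.46 |
| 17% | 4(20/17)² = 5.54, P = 0.76 | 9(15/17)² = 7.01, P = 0.36 |
| 19% | 4(20/19)² = 4.43, P = 0.65 | 9(15/19)² = 5.61, P = 0.22 |

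At each of these CVs the IQC level is more likely to pass than fail, and the pool is more likely to fail than pass.

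**Step 3: what tightening the IQC limit would cost**

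The probability that at least one of three independent levels fails is 1 − P³.

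| Assumed true CV | below 20%, n = 5 | below 15%, n = 5 | below 15%, n = 10 |
|---|---|---|---|
| 10% | 1 − 0.997³ = 0.01 | 1 − 0.939³ = 0.17 | 1 − 0.984³ = 0.05 |
| 12% | 1 − 0.975³ = 0.07 | 1 − 0.819³ = 0.45 | 1 − 0.880³ = 0.32 |

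Simulating with the mean estimated rather than fixed gives 0.46 and 0.08 in place of 0.45 and 0.07 (12%, n = 5), so the approximation is adequate. If the three levels share runs, their results are positively related and the chance of at least one failure is somewhat lower than shown.

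**The case against.** The strongest reply is that these are two experiments with two rules, and the laboratory can carry out both without ambiguity. The IQC is loaded on Mitra devices. The low pools are not said to be, and Sample analysis applies the LC-MS/MS creatinine method to serum as well as to capillary blood. The IQC results may therefore carry device-loading variance that the pool results do not. The 20% figure also recurs for recovery, the other test on QC material, which suggests a deliberate tier. The reason may lie in the departmental protocols, which are not shown.

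Much of this stands. A reader might infer that the plan sets two conflicting limits for one result, or that one of the two figures is a slip. The documents support neither reading: the materials differ, the LLOQ rule is never applied to IQC, and a QC tier is possible.

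The inverted order remains. The protocol does not use material or a tier to explain it, the general reference to outside recommendations gives no reason, and the Methodology section itself ties the LLOQ to precision studies. If imprecision does fall as concentration rises, IQC levels above a qualifying pool would normally be under 15% anyway. That makes the affected band less likely to be reached, but it does not explain a looser limit there.

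The wording of the LLOQ as the level meeting its limit is a small matter, since lower limit already implies the lowest.

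**Conclusion.** The concern holds as an unexplained inversion of two acceptance limits, and it is minor. The between-batch limit at the IQC levels is 5 percentage points looser than the one that defines the LLOQ. An IQC level with a CV from 15% to just under 20% is accepted although that CV could not define a quantifiable level. This conclusion rests on comparing the stated limits. The pass probabilities only illustrate it and depend on assumed true CVs, normal replicates and the reading of the replicate counts given above.

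A reader might also infer that the venous-capillary comparison is undermined. The documents do not support that: the 50-pair minimum and the Bland-Altman analysis are not derived from these limits. The effect is confined to acceptance of the creatinine assay, and nothing in the protocol shows whether the affected band will be reached.

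**What to change.** In Data Analysis, Creatinine method evaluation, set the between-batch precision limit at the IQC levels no looser than the LLOQ limit, that is, a CV below 15%. Do this before any validation data are seen, so that the limit cannot be chosen to fit them. The present sentence covers within-batch CV too, so the new wording should say which limit applies to each. In the LLOQ sentence, define the LLOQ as the lowest pool that meets its limit.

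This is a wording change, but it makes the test harder to pass. With the minimum of 5 replicates, a method with an assumed true CV of 10% or 12% would fail at one or more of three levels about 17% or 45% of the time, against about 1% or 7% now. Using 10 between-run IQC replicates, the number already planned for the pools, lowers this to about 5% or 32%. That step is optional and needs 5 × 3 = 15 more devices, assuming one device per analysis.

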#### **Sample collection comparison**

All samples will be analysed in duplicate and the results averaged. Passing-Bablok regression and Pearson correlation coefficient will be used to compare and assess correlation of the results of venous and capillary samples. Bland-Altman analysis will assess agreement and determine presence of any bias between the results obtained from venous and capillary sample collection. 95% confidence intervals will be calculated. Statistical analysis will be performed using the Analyse-It add-in for Microsoft Excel.

Stability: Samples will be analysed in duplicate and the results averaged. Means of each group will be

calculated and compared to baseline. Differences of  $\pm 15\%$  will be deemed acceptable.

**Effect of haematocrit concentration:** The 4 samples will be analysed in duplicate and the results averaged. Differences of 15% will be deemed acceptable and this would confirm samples collected using Mitra® devices are unaffected by differing haematocrit concentrations.

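### The creatinine linearity rule compares dilution means with each other and names no expected concentration, so as written a linear assay fails it and a flat response passes

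*Protocol*

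**What the plan says.** The Methodology section on creatinine method evaluation describes the samples: "Linearity will be determined by performing dilutions of the creatinine standard material to prepare an extended standard curve". It gives neither the number of levels nor the dilution factors.

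The Data Analysis section on creatinine method evaluation describes the measurement, "The diluted creatinine standards will be analysed in duplicate and plotted against the concentration to give the" r² value, and then gives the acceptance rule: "Means should be within 15% of each other to confirm linearity". No acceptance limit is set for r², so this sentence is the only criterion for linearity.

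The opening of Data Analysis refers outward in general terms: "Statistical analysis will be performed based on CSLI recommendations and departmental protocols". It names no comparator for linearity.

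Neighbouring rules do name theirs. Stability means are "calculated and compared to baseline", and recovery is judged against a target, "with the recovery being expressed as a percentage with an acceptability of 100±20" per cent.

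**The concern.** A linearity check asks whether the reading rises in proportion to concentration. A rule that wants the means of different concentrations to be close to one another asks for nearly the opposite. The analyst therefore cannot apply the sentence as it stands and has to choose a criterion, possibly with the data in view.

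Two sound criteria are available: each mean against its assigned concentration, or dilution-corrected means against each other. They can give different verdicts on the same data.

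At stake is whether, and over what range, the new LC-MS/MS creatinine method is called linear. Developing and validating that method is a stated objective of the study.

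**Working it through.** There is no derived figure in the protocol to reproduce. The 15% is a stated limit, so the check is to apply the rule to data whose linearity is known.

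**Inputs.** From the protocol: the 15% limit, duplicate measurement, a series of dilutions, and the precision rule "A CV less than 20% will be deemed acceptable". Assumed, because the protocol does not give them: six two-fold levels, CVs of 5% and 8%, normal error, and the size of any calibration bias.

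**1. Literal rule, perfectly linear assay, no noise.**
- If 15% is taken of the lowest mean, highest/lowest may be at most 1.15.
- If it is taken of the highest mean, highest/lowest may be at most 1/0.85 = 1.18.
- One two-fold step gives (2 − 1)/1 = 100% of the lower mean, or (2 − 1)/2 = 50% of the higher. It fails.
- Six two-fold levels: highest to lowest is 32 to 1, a difference of 31/32 = 96.9% of the higher. It fails with r² = 1.
- Five equal steps from 20% to 100%: the overall difference is 80% of the highest, and even the closest neighbours (80 and 100) differ by 20%. It fails.

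**2. Literal rule, no response to concentration.** Means of 100, 102, 98, 101 and 99 at nominal 20, 40, 60, 80 and 100 have a spread of (102 − 98)/98 = 4.1%. They pass, although r² is 0.09 and the lowest level reads 400% too high.

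**3. r² does not fill the gap.** Take a saturating response y = x/(1 + x/1500), starting at x = 1000 and halving five times. The top two levels read 40% and 25% low, yet r² is 0.982. With no limit stated, r² decides nothing.

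**4. How the two sound readings differ.** For a linear assay with proportional bias b, the chance that all six duplicate means fall within ±15% of the assigned value is

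[Φ((0.15 − b)/s) − Φ((−0.15 − b)/s)]⁶, with s = (1 + b) × CV/√2.

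- b = 0, CV 8%: s = 0.0566, 0.15/s = 2.65, per level 0.992, and 0.992⁶ ≈ 95%.
- b = +10%, CV 5%: s = 1.10 × 0.05/√2 = 0.0389. The upper limit is at 0.05/0.0389 = 1.29 and the lower term is negligible, so per level 0.901, and 0.901⁶ ≈ 53%.

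For dilution-corrected means compared with each other, simulation (400,000 runs) gives the rates below. The lower figure takes 15% of the lowest mean and the upper takes 15% of the highest. A constant proportional bias cancels.

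| Assumed case | Against assigned concentration | Corrected means against each other |
|---|---|---|
| No bias, CV 5% | >99.9% | 94–98% |
| No bias, CV 8% | 95% | 50–67% |
| No bias, CV 20% (the protocol's precision limit) | 13% | 2–4% |
| +10% bias, CV 5% | 53% | 94–98% |

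Neither reading is uniformly stricter. With no bias, comparison with the assigned value is the more lenient; with a 10% bias at a CV of 5% the order reverses.

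**5. A third form: each corrected mean against the overall corrected mean.** Measured from the mean of six levels, s shrinks by √(5/6) = 0.913. At CV 8% the limit is at 2.65/0.913 = 2.90, giving per level 0.996 and about 98% for all six (treating levels as independent). Proportional bias cancels here too.

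**The case against.** The strongest reply is that nobody would apply the sentence literally. The preceding sentence plots results against concentration, the laboratory is accredited to ISO 15189, and the analysis refers to outside recommendations and departmental protocols. On that view the defect is an unnamed comparator, not a wrong analysis. The point about likely intent stands and keeps the weight low. It does not remove the finding: the protocol fixes a specific numerical rule, that rule gives the wrong answer if followed, and nothing else in the document corrects it. For the same reason it is not a detail left to a later analysis plan.

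Reading the sentence as agreement between duplicates does not help. The text says means, and duplicate agreement tests repeatability; the saturating curve above would pass with identical duplicates.

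A second objection concerns the remedy. Agreement with the assigned concentration tests calibration bias as well as linearity, and the protocol judges bias separately through recovery and the comparison with the enzymatic assay. A method whose standards all read 18% high would be linear and, with an equal recovery of 118%, would pass the recovery rule, yet it would fail a ±15% rule against assigned values. This objection stands in full, so the choice has to be made openly.

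A reader might infer from the no-bias rows that comparison with assigned values is simply the easier criterion. The +10% row shows that this holds only when calibration bias is small.

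**Conclusion.** The concern holds as a minor correction. The only linearity criterion is wrong as written for a dilution series: any series spanning more than about 1.15- to 1.18-fold fails even if perfectly linear, and a flat response passes. That result needs no assumption about levels or CV. The pass rates do: they rest on six levels in duplicate, normal error, and assumed CVs and bias. The 20% CV is the protocol's acceptance ceiling, not expected performance.

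Two stronger readings are not supported. One is that the linearity assessment will actually fail or that the creatinine method cannot be validated; a sound comparison is probably intended, and recovery and the enzymatic comparison may still reveal concentration-dependent bias. The other is that the venous–capillary results or patient care are compromised. The rule does not apply to tacrolimus and does not enter the venous–capillary agreement analysis, and no patient effect follows from it.

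**What to change.** Replace the acceptance sentence in Data Analysis, creatinine method evaluation, with:

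> At each dilution the mean of the duplicates must lie within ±15% of the concentration assigned to that dilution; the linear range is the span of consecutive levels that meet this.

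The noise-free linear series then deviates by 0% at every level and passes. The flat response (up to +400%) and the saturating curve (−40% and −25% at the top two levels) fail.

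If bias is to be judged only by the recovery and method-comparison checks, write instead:

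> Each dilution-corrected mean must lie within ±15% of the overall dilution-corrected mean.

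**Cost.** One sentence, with the same measurements and no extra runs. The first form can reject a linear assay with a constant proportional bias, and an imprecise linear assay can lose a level by chance (all six pass in 95% of runs at a CV of 8% and 13% at 20%, with no bias). The second form ignores constant bias but is less exact about where curvature lies. In the saturating example the corrected ratios 0.60, 0.75, 0.857, 0.923, 0.96 and 0.98 average 0.845, so the top level is flagged (−29%), the second is not (−11%), and the lowest is flagged too (+16%).

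### The creatinine LLOQ is set by between-batch CV alone; no limit is placed on how far the low pool's mean may lie from its true value

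*Protocol*

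**What the plan says.** The Methodology section on creatinine method evaluation bases the LLOQ on repeatability: "Precision studies will be used to determine the LLOQ". The material is described only as follows: "Low patient pools will be prepared to give appropriate concentrations". Replication is given as "Samples will be analysed 10 times within the same analytical run and 10 times between runs". No assigned or reference value for the pools is mentioned, and the pool matrix is not stated.

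The matching part of Data Analysis says "LLOQ: Mean, SD and %CV will be calculated" and then gives the rule: "LLOQ will be defined as the level with a between batch precision of <15" per cent.

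The checks closest to trueness sit elsewhere in the protocol:

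- **Recovery:** the mean of three runs at every QC concentration, judged against 100±20%. The material is separate from the low pools: "blank samples will undergo sample preparation steps and will be spiked with the 3 different levels of creatinine QC".
- **Linearity:** diluted creatinine standards, with means to lie within 15% of each other.
- **Method comparison against the Roche enzymatic assay:** Passing-Bablok regression and Bland-Altman analysis on at least 50 patient samples plus EQA samples, with no numerical bias limit.
- **EQA:** 20 clinical chemistry scheme samples analysed for creatinine.

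**The concern.** A limit of quantitation claims that a result at that level can be reported as a number. That needs the result to be close to the truth as well as repeatable. The protocol computes the mean of each low pool, which is the quantity that would show whether it is close, and then does not use it.

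The omission matters because of how a CV is built. It is the SD divided by the measured mean. If every result is multiplied by the same wrong factor, SD and mean scale together and the CV does not move. If every result carries the same added background, the mean rises, the SD stays put and the CV falls. In the first case the rule is blind to the error; in the second the error helps the pool to pass.

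At stake is the lower end of the range that the validation will claim. Validating the LC-MS/MS method is the first stated objective, and the protocol intends home sampling to enter routine care.

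**Working it through.** The protocol gives no LLOQ value, SD or pool concentration, so there is no figure of its own to reproduce. From the document come the 15% limit, the 10 between-run results per pool, the 20% recovery limit and the 15% limit used for linearity, carryover and stability. All concentrations, SDs and biases below are assumptions chosen to show direction and size.

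**Step 1: one worked pool.** Assume a true value of 20 µmol/L and a between-batch SD of 4. The true CV is 4/20 = 20%, so the pool should fail. Add a constant offset and leave the SD unchanged:

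| Offset (µmol/L) | Measured mean | Observed CV | Bias | CV rule |
|---|---|---|---|---|
| 0 | 20 | 4/20 = 20.0% | 0% | fail |
| +7 | 27 | 4/27 = 14.8% | 7/20 = +35% | pass |
| +10 | 30 | 4/30 = 13.3% | 10/20 = +50% | pass |

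**Step 2: the general relation.** With true CV c (in per cent) and constant relative bias b, the observed CV is c/(1 + b). It falls below 15% once b exceeds c/15 − 1:

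- c = 18%: 18/15 − 1 = 20% bias
- c = 20%: 20/15 − 1 = 33% bias
- c = 25%: 25/15 − 1 = 67% bias

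**Step 3: the rule with 10 results.** The observed CV is itself an estimate. The chance that sample SD over sample mean falls below 15% was simulated (200,000 runs, normal errors, n = 10).

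| True CV | Type of bias | No bias | +20% | +50% | +100% |
|---|---|---|---|---|---|
| 10% | proportional | 0.98 | 0.98 | 0.98 | 0.98 |
| 20% | proportional | 0.18 | 0.18 | 0.18 | 0.18 |
| 20% | constant, SD fixed | 0.18 | 0.40 | 0.75 | 0.98 |
| 25% | constant, SD fixed | 0.05 | 0.14 | 0.40 | 0.83 |

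Proportional bias leaves acceptance unchanged. Constant positive bias raises it steeply.

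**Step 4: would the recovery limit catch it?** An offset of +7 is 20% of 35 (7/35 = 20%). If it appears in the spiked blanks and is the only error, it stays within 100±20% at any QC level of 35 µmol/L or more, although it is 35% at 20 µmol/L. The protocol does not give the QC levels, so whether the lowest one would expose it cannot be told.

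**Step 5: the same simulation with a limit on the mean added.**

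- Levels reading +50% or +100%: accepted with probability 0.00, at true CV 10% or 20%, under a ±15% or a ±20% limit.
- Unbiased level with CV 10%: still accepted about 98% of the time under either limit.
- Level reading +20% with CV 10%: accepted about 6 to 9% of the time under ±15%, and about half the time under ±20%.

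**The case against.** The strongest reply is that trueness is examined in other parts of the same validation. Background in the blanks would inflate recovery, most of all at the lowest QC level. The Passing-Bablok intercept estimates a constant difference from the Roche method. Bland-Altman analysis and the EQA samples look at bias too, and the protocol says what follows if a clinically significant bias is found. This stands in part: a large bias could well be noticed. But none of these checks is run on the low pools, and none is a condition for declaring the LLOQ.

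Second, Data Analysis refers in general terms to outside recommendations and departmental protocols, and an analysis plan may exist that is not shown. Either could hold further LLOQ criteria. But the protocol does not leave the definition open: it states a rule with its threshold, and a general reference does not alter that rule.

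Third, the mechanism has limits, and this stands. A reader might infer that the rule favours upward-biased levels in general. It does so only for an additive offset that adds no variance. Proportional bias leaves the pass rate unchanged, and a background that varies from run to run would raise the SD and could cancel the effect.

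Fourth, a reader might infer from the missing word 'lowest' that the LLOQ is not identified. That goes too far. The term itself means a lower limit and the protocol prepares low pools for it, so this is only a point of wording.

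**Conclusion.** The point holds as a gap in the acceptance rule: a low pool that reads materially wrong can be declared quantifiable because only its CV is judged. With a true CV of 20%, a constant bias of 33% is enough to bring the expected CV down to the limit. With 10 results, a bias of +50% raises the chance of acceptance from 0.18 to 0.75. These figures rest on assumed SDs and offsets, normal errors and an SD that the offset does not change.

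A reader might go further and infer that the validation claim will be wrong. The documents do not support that. They give no evidence of a background or interference, and the other checks may reveal one. The practical effect is probably small, since creatinine in these patients may seldom lie near the LLOQ; the protocol gives no concentrations with which to test this. The venous-capillary comparison is not shown to change. This is a minor improvement, worth making because it is cheap.

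**What to change.** Replace the LLOQ sentence in Data Analysis with wording such as: *The LLOQ is the lowest pool with a between-batch CV below 15% and a mean within ±15% of its assigned value. The assigned value comes from dilution of a higher-level pool or from a known addition of creatinine.* This also settles the point of wording.

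The limit on the mean should be fixed in advance. The ±15% matches the figure already used for linearity, carryover and stability. The ±20% recovery limit is the other candidate, but it would let a +20% level through about half the time.

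The diluent and pool matrix should be named. Dilution exposes a constant offset, because the offset is a small share of the higher-level result from which the value is assigned. It does not expose proportional bias, which carries through to the assigned value and cancels; known addition, or the existing method comparison and EQA samples, must cover that.

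The Roche serum result should not be the default assigned value. It would bring the method difference, and for a whole-blood pool also the specimen difference, into the LLOQ, and those are what the study sets out to measure.

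The cost is one sentence and some care in preparing the pools; the 10 between-run results are already planned. The downside is that the reported LLOQ may be slightly higher.
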